5.9.2 Blinding

This is an open-label study; hence there will be no requirement for blinding of study personnel at site and sponsor/CRO.

The study centre will receive a randomisation schedule to be used by the centre for randomisation of matched-pair clusters. This schedule will have a randomisation number for a matched pair of clusters followed by the study group (test/control) for intervention within clusters.

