9.3.2. Primary Analyses

The primary efficacy variable of the study is the number of ill days. The number of ill days is defined as number of days a subject is ill because of GI and/or respiratory illnesses as diagnosed by study physician, as per the criteria defined in Section 6.11.1 and 6.11.2, over the intervention period.

For this variable, primary analysis will be performed on participants in ITT population who have completed the entire study for 9 months.

The null hypothesis of interest is:

H₀: There is no difference in the number of ill days.

The alternative hypothesis of interest is:

H₁: There is a difference in the number of ill days.

The number of ill days will be summarised in terms of number (N), mean, standard deviation, minimum, and maximum for both the treatment groups.

The number of ill days will be analysed using the analysis of variance (ANOVA). The ANOVA will have treatment, cluster (school), and gender as fixed effects.

Adjusted means, 95% confidence intervals, within treatment p-values for each treatment group, treatment group difference, 95% confidence interval of the difference and the between-treatment p-values based on the statistical model described above will also be presented.

All statistical tests of hypotheses will be two-sided and will employ a level of significance of $\alpha = 0.05$.

The simulated data used for the sample size calculations were based upon the assumption of a Poisson distribution per study treatment. However, on observation of these simulated data, it was considered that these Poisson distributions were not heavily skewed and, as a result, normal distributions may be assumed. Consequently, a normality assumption has been adopted for both the generation of sample size and the intended approach to the statistical analysis. However, the assumptions of normality and homogeneity of variance will be investigated and violation of these assumptions may be overcome using suitable transformation (for example, log or square root). If transformed data is also non-normal, then alternative analyses relevant to Poisson distributed data will be investigated (further details will be

 GlaxoSmithKline	Document Name	Clinical Study Protocol 204477		
	Type	Version	Document Identifier	Effective Date
	eldo_clinical_doc	5.0; Most-Recent; Effective; CURRENT	090032d580daa95e	10-Oct-2017 06:16:49
	Reason For Issue	Auto Issue		

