1.4 Sample Size Calculation

The primary efficacy variable of the study is the total number of ill days due to GI and respiratory illnesses. The sample size has been calculated based on the assumption of an average of 7 ill days in the control group with a difference of 10% between the treatments.

Years Lost due to Disability (YLD) is a measure of the burden of disease from its morbidity. Below are data that are specific to India: As per the data from Global Burden Disease, WHO 2010 study (GBD, WHO, 2012; IHME, 2013) and Census India, 2011, YLD per child in the 5-9-year age group, due to diarrhea, LRTIs, other infectious disease and nutritional deficiencies is 8.274 days/child per year or 6.21 days/child per 9 months.

Thus, based on above data, approximately 7 ill days due to GI and respiratory illnesses per 9 months has been assumed in this proposed study population of 7-10 year olds.

The sample size is based on the primary endpoint. No sample size considerations have been taken into account for secondary objectives.

The simulated data were also used based upon the assumption of a Poisson distribution per study treatment. On observation of these simulated data, it was considered that these Poisson distributions were not heavily skewed and, as a result, normal distributions may be

assumed. Consequently, a normality assumption has been adopted for both the generation of sample size and the intended approach to the statistical analysis.

Because of assumption of Poisson distribution, estimates of variability were calculated as square root of mean.

Mean of control was assumed to be 7.0 and standard deviation (SD) was 2.65, mean of test group was 6.3 and SD was 2.51. To be able to achieve 80% power, 215 participants per treatment arm (Total = 430) will be required to complete the study in case of individual randomisation. This assumes 5% level of significance (two tailed t-test).

As this study is using cluster randomization, and design effect (DE) needs to be considered for sample size calculations. Scientific literature suggests, DE due to cluster sampling strategy can be assumed to be 1.5 [Rosner, B, 1986]. Same has been assumed in one study, which used three-stage systematic cluster sampling [Dandona R *et al*, 2008].

Using the following formula from Hemming *et al*, 2011:

$$N^* = N \times DE$$

Where N^* = Number of participants required for cluster randomized trial

N = Number of participants required for individual randomization

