DE = design effect

And assuming DE to be 1.5, the number of evaluable participants completing the study required would be 323 per arm (Total=646).

To allow for 30% drop-out rate, a total of 924 participants will be randomized.

Approximately 1300 participants will be screened to randomize approximately 924 participants in order to obtain 646 participants completing the study.

2 Planned Analyses

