4.4.1.2 Statistical Hypothesis, Model, and Method of Analysis

For the primary variable, primary analysis will be performed on participants on the mITT population.

The null hypothesis of interest is:

H0: There is no difference between the numbers of illness days for the product groups.

The alternative hypothesis of interest is:

H1: There is a difference in between the numbers of illness days for the product groups.

The number of ill days will be analysed using the analysis of variance (ANCOVA) model. The ANCOVA will have cluster (school) as a random effect, product group and gender as fixed effects and baseline IDDS as a covariate.

Adjusted means, 95% confidence intervals (CI), within product group p-values for each product group, product group difference, intracluster correlation, 95% confidence interval of the difference and the between-product group p-values based on the statistical model described above will also be presented ([Table 14.2.2.2](#)).

All statistical tests of hypotheses will be two-sided and will employ a level of significance of $\alpha = 0.05$.

The simulated data used for the sample size calculations were based upon the assumption of a Poisson distribution per product group. However, on observation of these simulated data, it was considered that these Poisson distributions were not heavily skewed and, as a result, normal distributions may be assumed. Consequently, a normality assumption has been adopted for both the generation of sample size and the intended approach to the statistical analysis.

However, the assumptions of normality and homogeneity of variance will be investigated and violation of these assumptions may be overcome using suitable transformation (for example, log or square root or Poisson regression using Proc Genmod) or by performing appropriate non-parametric tests (e.g., Van Elteren, rank ANCOVA).

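### The log and Poisson fallbacks for the primary test have no zero, dispersion or school provision; Poisson as written gives about 11% type I error at the plan's own design effect

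*SAP*

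**What the plan says.** **Primary model.** SAP 4.4.1.2 analyses ill days with school as a random effect, product group and gender as fixed effects, and baseline IDDS as a covariate. Amendment 1 (SAP section 5) moved school from fixed to random and says a valid analysis needs adjustment for intracluster correlation. It says this for the ANCOVA models only.

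**Fallback.** The same section says a violation of normality or homogeneity may be dealt with by "suitable transformation (for example, log or square root or Poisson regression using Proc Genmod) or by performing appropriate non-parametric tests", with Van Elteren and rank ANCOVA as examples of the last. It gives no test or threshold for a violation, no order among the options, no constant for log of zero, and no scale or school term for the Poisson model.

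**Protocol.** Protocol 9.3.2 set an order: transform first, then "If transformed data is also non-normal, then alternative analyses relevant to Poisson distributed data will be investigated", then non-parametric tests. It promised more detail on the Poisson step in the SAP. The SAP does not supply it and does not repeat the order.

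**Endpoint.** SAP 4.4.1.1 counts every day of an episode, including symptom-free days inside it.

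**Blinding.** Protocol 5.9.2 describes an open-label study, "hence there will be no requirement for blinding of study personnel at site and sponsor/CRO".

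**The concern.** Poisson regression takes the variance to equal the mean and the children to be independent. Neither is likely here. Days arrive in episodes: if episodes occur at random and each lasts L days, the mean is λL and the variance λL², so the variance/mean ratio is L. Children are also grouped in four schools. The primary model carries the school term; the Poisson option, read as written, does not. Its standard error would be too small.

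A log transform without a constant cannot use a child with zero ill days, and zero is the best possible outcome on this endpoint.

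Protocol 9.2.3 makes this one comparison the success criterion. With no stated trigger, the model that decides success could be settled after results are visible by arm.

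**Working it through.** **1. Reproduce the plan's sample size.** Planning values from SAP 1.4: "Mean of control was assumed to be 7.0 and standard deviation (SD) was 2.65, mean of test group was 6.3 and SD was 2.51". The target there is a two-sided t-test at 5% with power of 80%, for which the SAP states 215 per arm.

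- Pooled SD = √[(2.65² + 2.51²)/2] = 2.581; difference = 7.0 − 6.3 = 0.7.
- The normal approximation gives 214 per arm. The exact noncentral t gives 215 (power 80.1%), as stated.
- 215 × 1.5 = 322.5, so 323 per arm. 323/0.70 = 461.4, so 462 per arm and 924 in total, as stated.

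The variance in this calculation is the Poisson one: "Because of assumption of Poisson distribution, estimates of variability were calculated as square root of mean". The only allowance for extra variation is the 1.5-fold inflation for clustering, which takes the evaluable total to 646.

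**2. Plain Poisson, using only the documents' figures.** If the true variance of the treatment contrast is φ times the Poisson variance, the standard error is too small by √φ and the two-sided type I error at a nominal 5% is 2[1 − Φ(1.96/√φ)]. With φ = 1.5:

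- √1.5 = 1.225, so the standard error is 18% too small (1/1.225 = 0.816).
- Type I error = 11.0%. A simulation of Poisson counts in four schools of 162, with the intracluster correlation set to give a design effect of 1.5, gave 11.2% (20,000 runs).

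A design effect of 1.5 implies an intracluster correlation of only about 0.5/160.5 = 0.003 at 646/4 = 161.5 children per school.

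**3. Adding overdispersion (assumed).** The documents give no variance/mean ratio other than 1, so a range is shown. School is left out here.

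| Assumed variance/mean ratio | Type I error, plain Poisson |
|---|---|
| 2 | 16.6% |
| 3 | 25.8% |
| 5 | 38.1% |
| 8 | 48.8% |

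Simulated negative binomial counts with a ratio of 4.5 and a design effect of 1.5 together gave 45%.

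**4. Zeros lost under log(y) without a constant.** Under Poisson, P(0) = exp(−μ). Under a negative binomial, P(0) = [k/(k + μ)]^k, and the variance/mean ratio is 1 + μ/k. Per 323 children:

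| Model | Control, mean 7.0 | Test, mean 6.3 |
|---|---|---|
| Poisson (planning) | 0.09%, 0.3 children | 0.18%, 0.6 children |
| k = 3.5 (control ratio 3, assumed) | 2.1%, 7 children | 2.7%, 9 children |
| k = 2 (control ratio 4.5, assumed) | 4.9%, 16 children | 5.8%, 19 children |
| k = 1 (control ratio 8, assumed) | 12.5%, 40 children | 13.7%, 44 children |

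**5. What the loss of zeros can cost.** This depends on how the product works. The simulations use 323 per arm, negative binomial counts, ratios of 3 and 5, and no school effect.

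- If 10% of test children become illness-free, power is about 46% and 32% untransformed, but about 5% with log and zeros dropped. Square root gives about 87% and 68%.
- Under the planned shift from 7.0 to 6.3, log with zeros dropped gives 46% and 28%, against 50% and 34% untransformed.

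**The case against.** The SAP commits to nothing here: it says a violation *may* be handled this way and offers examples. Several stronger readings go beyond the text.

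- **That the SAP moves to a log that deletes every child with zero days.** Square root and the rank methods are also listed, and both keep zeros. Deletion needs log(y) with no constant. The SAP's only detail on logs (base 10 and geometric means, for certain laboratory endpoints in 4.4.2) mentions no constant, but does not exclude one. At the planning means the loss is under one child per arm.
- **That Poisson would be reached only when it is wrong.** In a check with 646 true Poisson counts at means 7.0 and 6.3, a Shapiro-Wilk test on the residuals rejected normality in all 1,000 runs. The switch can therefore be triggered when Poisson is right for the children's counts.
- **That no order exists.** Protocol 9.3.2 gives one, and SAP section 5, which lists changes from the protocol, records no change to it. The order can be read as still standing.
- **That the choice will be made unblinded, or by the smallest p-value.** Protocol 5.9.2 says blinding is not required. SAP sections 2.2, 4 and 4.1.2 describe blinded review and later release of codes, but do not assign the model choice to that review. The stated trigger is an assumption violation, not a p-value.
- **That the untransformed count should be the only permitted test.** In the illness-free scenario above, square root has far more power, so this is a trade-off and not a correction.

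GENMOD can also fit a scale parameter or GEE. The SAP neither specifies nor rules these out, so a plain Poisson fit is the literal reading rather than a stated intention.

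What stands is that the SAP names a specific model for the primary endpoint without the school adjustment it calls necessary elsewhere, and without the Poisson detail the protocol promised.

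**Conclusion.** The concern holds as a defect in the named fallbacks; it is not a defect in the planned mixed model. A Poisson model fitted as written would have about 11% type I error at the documents' own design effect, and about 17% to 49% if the variance/mean ratio is 2 to 8. The first figure needs only the design effect of 1.5 and a model that omits school. The second rests on assumed ratios, made plausible by the counting of whole episodes. Log without a constant matters only under overdispersion: negligible at the planning means, roughly 2% to 12% of control children at assumed ratios of 3 to 8. The SAP leaves the trigger open in an open-label trial, so the choice could be made with allocation known; the documents do not say that it will be.

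**What to change.** In SAP 4.4.1.2:

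1. Replace the GENMOD Poisson option with one pre-named overdispersed count model, negative binomial or quasi-Poisson. Keep school, gender and baseline IDDS alongside product group, and name a small-number-of-clusters method. Four schools in two arms leave 4 − 2 = 2 between-school degrees of freedom, so an uncorrected robust standard error would not be enough.
2. Remove log, or require a form that keeps zeros, such as log(y + 1).
3. Name that count model as the single fallback and state its trigger before any data are viewed by allocation. A bare normality p-value is a poor trigger, because at this sample size it rejects even true Poisson data.
4. Report the planned untransformed mixed model alongside the fallback if the fallback is used.

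For episode frequency and absenteeism (SAP 4.4.2), require only that any transformation keeps zeros. Neither log nor Poisson is named there, so nothing needs removing.

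The cost is SAP wording and slightly more analysis work. Intervals from the fallback will be wider than from plain Poisson, reflecting variation that the plain model ignores.

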4.4.1.3 Supportive Analyses

As a part of sensitivity analysis a Mixed Model Repeated Measure (MMRM) model will be used. MMRM model will be just an analysis including multiple visits with defined structure of correlation among visits. In this study unstructured covariance matrix will be used. The number of ill days will be analysed using model with cluster (school) as a random effect; product group, gender, and visit and (product group and visit) interaction as fixed effects and baseline IDDS as a covariate.

This will be conducted on the primary efficacy endpoints on the ITT population ([Table 14.2.2.2a](#)).

4.4.2 Secondary Efficacy Variables

The analysis of secondary efficacy variables will be on the mITT population.

The secondary efficacy variables are:

- **Frequency of GI and Respiratory illness**

Frequency of GI and respiratory illnesses defined as total number of illness episodes of GI and/or respiratory illnesses, divided by duration of intervention in month, where each episode is defined as each incidence of illness followed by at least 3 symptom free days will be summarized in a table for the product groups (Table 14.2.3.1).

The frequency of GI and respiratory illnesses will be calculated as following –

Frequency (per month) = No of episodes X 30/ Number of days between first (BV) and last visit

Frequency of GI and respiratory illnesses will be analysed together using analysis of covariance (ANCOVA) model. The model will include cluster (school) as a random effect; fixed effects for product group and gender; and baseline IDDS as a covariate. Adjusted means, 95% confidence intervals, intraclass correlation, within product group p-values for each product group, product group difference, 95% confidence interval of the difference and the between-product group p-values based on the statistical model described above will also be presented (Table 14.2.3.2).

The assumptions of normality and homogeneity of variance will be investigated and violation of these assumptions may be overcome using suitable transformation or by performing sensitivity analysis or by appropriate non-parametric tests (e.g., Van Elteren, rank ANCOVA).

- **Analysis on Severity of GI and Respiratory illness:**

Frequency and percentages of severity episodes of GI and respiratory illnesses will be summarized in a table together and also separately (Table 14.2.4.1). If an episode comprises of occurrences of different severities, then the highest severity will be considered as the overall severity. Severity grades will be displayed in the tables for the GI and respiratory illness as mentioned in the Appendix 5 of the Protocol version 5.0.

Frequencies of severity (Mild, moderate, or severe) episode between product groups will be compared using Chi-Square test (if frequencies are greater than 5%). If frequencies are $\leq 5\%$ in any product group, then these will be compared using Fisher's exact test between product groups (Table 14.2.4.1).

- **Analysis of School absenteeism due to GI and Respiratory illness:**

Descriptive statistics (n, mean, and median, SD, minimum and maximum) will be provided for school absenteeism due to GI and respiratory illnesses (Table 14.2.5.1).

School absenteeism due to GI and respiratory illnesses will be analysed together using analysis of variance (ANCOVA) model. The model will include cluster (school) as a random effect; fixed effects for product group and gender; and baseline IDDS as a covariate.

Adjusted means, 95% confidence intervals, within product group p-values for each product group, product group difference, intraclass correlation, 95% confidence interval of the difference and the between-product group p-values based on the statistical model described above will also be presented ([Table 14.2.5.2](#)).

The assumptions of normality and homogeneity of variance will be investigated and violation of these assumptions may be overcome using suitable transformation or by performing appropriate non-parametric tests (e.g., Van Elteren, rank ANCOVA).

- **Analysis of Body Mass Index (BMI):**

Descriptive statistics (n, mean, and median, SD, SE, minimum and maximum) will be provided for BMI ([Table 14.2.6.1](#)). Change from baseline of BMI will be analysed using an analysis of covariance (ANCOVA) model. The model will include cluster (school) as a random effect; fixed effects for product group and gender; baseline BMI assessment recorded at screening visit and baseline IDDS as a covariate. Adjusted means, intraclass correlation, 95% confidence intervals, within product group p-values for each product group, product group difference, 95% confidence interval of the difference and the between-product group p-values based on the statistical model described above will also be presented ([Table 14.2.6.2](#)). The assumptions of normality and homogeneity of variance will be investigated and violation of these assumptions may be overcome using suitable transformation or by performing appropriate non-parametric tests (e.g., Van Elteren).

- **Analysis of Gut integrity/health as measured by Lactulose: Mannitol test and Urinary Neopterin test:**

Descriptive statistics (n, mean, and median, SD, SE, minimum and maximum) for the Lactulose: Mannitol and Urinary Neopterin will be provided in a table ([Table 14.2.7.1](#)). Change from baseline in gut integrity/health as measured by Lactulose: Mannitol test and Urinary Neopterin test will be analysed using an ANCOVA model.

The model will include cluster (school) as a random effect; fixed effects for product group and gender, baseline gut integrity/health assessment as a covariate. Adjusted means, intraclass correlation, 95% confidence intervals, within product group p-values for each product group, product group difference, 95% confidence interval of the difference and the between-product group p-values based on the statistical model described above will also be presented ([Table 14.2.7.2](#)).

The assumptions of normality and homogeneity of variance will be investigated and violation of these assumptions may be overcome using suitable transformation or by performing appropriate non-parametric tests (e.g., Van Elteren).

- **Analysis of Salivary IgA (sIgA):**

Descriptive statistics (n, mean, and median, SD, SE, minimum and maximum) for the sIgA will be provided (Table 14.2.8.1). Change from baseline of sIgA will be analysed using an ANCOVA model. The model will include cluster (school) as a random effect; fixed effects for product group and gender; baseline sIgA assessment as a covariate. Adjusted means, intraclass correlation, 95% confidence intervals, within product group p-values for each product group, product group difference, 95% confidence interval of the difference and the between-product group p-values based on the statistical model will also be presented (Table 14.2.8.2).

The assumptions of normality and homogeneity of variance will be investigated and violation of these assumptions may be overcome using suitable transformation (eg., log or square root) or by performing appropriate non-parametric tests (e.g., Van Elteren).

In case of logarithm transformation log base 10 will be used and additionally geometric mean will be provided for the descriptive statistics.

- **Analysis of Micronutrients from blood sample:**

Descriptive statistics (n, mean, and median, SD, SE, minimum and maximum) for the micronutrients (Vitamin A, B12, D (25 Hydroxy calciferol), E, folate, of the trace elements selenium, zinc, copper, and iron) concentration levels will be provided (Table 14.2.9.1).

Change from baseline in concentration levels of micronutrients (Vitamin A, B12, D (25 Hydroxy calciferol), E, folate, of the trace elements selenium, zinc, copper, and iron) will be analysed using an ANCOVA model. The model will include cluster (school) as a random effect; fixed effects for product group and gender; baseline assessments concentration levels and baseline IDDS as a covariate.

Adjusted means, intraclass correlation, 95% confidence intervals, within product group p-values for each product group, product group difference, 95% confidence interval of the difference and the between-product group p-values based on the statistical model will also be presented (Table 14.2.9.2).

The assumptions of normality and homogeneity of variance will be investigated and violation of these assumptions may be overcome using suitable transformation (eg., log or square root) or performing appropriate non-parametric tests (e.g., Van Elteren).

In case of logarithm transformation log base 10 will be used and additionally geometric mean will be provided for the descriptive statistics.

- **Analysis of serum variables from blood sample:**

Descriptive statistics (n, mean, and median, SD, SE, minimum and maximum) for the serum parameters (ferritin, serum-transferrin receptor (sTfR), C-reactive protein (CRP), and Alpha 1-acid glycoprotein (AGP)) will be provided (Table 14.2.10.1). Change from baseline in concentration levels of serum parameters C-reactive protein (CRP), and Alpha 1-acid glycoprotein (AGP) will be analysed using an ANCOVA model.

The model will include cluster (school) as a random effect; fixed effects for product group and gender; baseline assessments of each serum concentration levels as a covariate. Also, a separate ANCOVA model will be used to analyse change from baseline ferritin, serum-transferrin receptor (sTfR), with cluster (school) as a random effect; product group and gender as fixed effects and baseline assessment concentration levels, CRP and AGP concentration levels as covariates.

Adjusted means, intracluster correlation, 95% confidence intervals, within product group p-values for each product group, product group difference, 95% confidence interval of the difference and the between-product group p-values based on the statistical model will also be presented (Table 14.2.10.2).

The assumptions of normality and homogeneity of variance will be investigated and violation of these assumptions may be overcome using suitable transformation (eg., log or square root) or by performing appropriate non-parametric tests (e.g., Van Elteren).

In case of logarithm transformation log base 10 will be used and additionally geometric mean will be provided for the descriptive statistics.

- **Analysis of Individual Dietary Diversity Score (IDDS):**

Descriptive statistics (n, mean, and median, SD, SE, minimum and maximum) for the IDDS will be provided (Table 14.2.11.1). Also, change from baseline IDDS will be presented in a summary table by product group. Change from baseline in dietary diversity score will be analysed using an ANCOVA model. The model will include cluster (school) as a random effect; fixed effects for product group, and gender; baseline assessments at screening as a covariate.

Adjusted means, intracluster correlation, 95% confidence intervals, within product group p-values for each product group, product group difference, 95% confidence interval of the difference and the between-product group p-values based on the statistical model will also be presented (Table 14.2.11.2).

The assumptions of normality and homogeneity of variance will be investigated and violation of these assumptions may be overcome using suitable transformation (eg., log or square root) or by performing appropriate non-parametric tests (e.g., Van Elteren).

IDDS categories are defined as below –

1. ≤ 3 food groups – Lowest dietary diversity
2. 4 and 5 food groups – Medium dietary diversity
3. ≥ 6 food groups – High dietary diversity

Frequency and percentages for each category of IDDS will also be presented ([Table 14.2.11.3](#)).

Frequencies for each category between product groups will be compared using Chi-Square test (if frequencies are greater than 5%). If frequencies are $\leq 5\%$ in any product group, then these will be compared using Fisher's exact test between product groups ([Table 14.2.11.3](#)).

- **Analysis of energy, protein, carbohydrate and fat from 24-hour dietary recall survey:**

Descriptive statistics (n, mean, and median, SD, SE, minimum and maximum) for the Energy, Protein, Fat and Carbohydrate will be provided ([Table 14.2.12.1](#)).

Change from baseline of each assessment will be analysed using the ANCOVA model with cluster (school) as a random effect; product group and gender as fixed effects; baseline assessments for each responses as a covariate.

Adjusted means, intracluster correlation, 95% confidence intervals, within product group p-values for each product group, product group difference, 95% confidence interval of the difference and the between-product group p-values based on the statistical model will also be presented ([Table 14.2.12.2](#)).

The assumptions of normality and homogeneity of variance will be investigated and violation of these assumptions may be overcome using suitable transformation (eg., log or square root) or by performing appropriate non-parametric tests (e.g., Van Elteren).

